1.2.1 Primary estimand(s)

The estimand is the precise description of the treatment effect and reflects strategies to address events occurring during trial conduct which could impact the interpretation of the trial results (e.g. premature discontinuation of treatment).

The primary clinical question of interest is: What is the effect of inclisiran versus placebo on top of an ongoing individually optimized LLT on achieving the individual LDL-C target at Day 90 in very high risk and high risk participants as defined in the 2019 ESC/EAS guidelines for the treatment of dyslipidemias ([Mach et al 2020](#)).

The primary estimand is described by the following attributes:

1. **Population:** Adult participants categorized as very high risk or high risk as defined by the CV risk categories in the 2019 ESC/EAS guidelines for the management of dyslipidemias ([Mach et al 2020](#)) with elevated LDL-C despite being treated with the individual MTD of statin and, if applicable, also other LLT. Further details about the population are provided in Section 5 of the protocol
2. **Endpoint:** Proportion of participants achieving individual LDL-C target (< 55 mg/dL or < 70 mg/dL) at Day 90. The individual LDL-C target of the participants is determined according to their individual CV risk category.
3. **Treatment of interest:** Inclisiran, compared to placebo, both on top of an ongoing individually optimized LLT. Randomized treatments are the investigational treatment inclisiran or the placebo control treatment. In both treatment arms, participants receive an individually optimized rosuvastatin therapy for reaching the individual LDL-C target and tolerability. If required to achieve their LDL-C target, further individually optimized LLT can be administered. Additional information about the investigational treatment and control treatment are provided in Section 6 of the protocol.
4. **Summary measure:** The odds ratio of achieving individual LDL-C target at Day 90 compared between treatment arms. A larger proportion of participants indicates a superior outcome.

1.2.2 Secondary estimand(s)

The population and the treatment of interest associated with the secondary estimand are the same as for the primary estimand.

The secondary estimands are defined by the evaluation of treatment effect on the following endpoints and summary measures:

- Relative change (percentage change) from baseline to mean LDL-C level over the double-blind study period (averaged over all post baseline visits).
- Proportion of participants experiencing at least one muscle-related AE as defined in the SMQ rhabdomyolysis / myopathy from Day 1 to Day 360.
- Annualized number of days participants experiencing self-reported pain from Day 1 to Day 360.
- Change from baseline in SF-BPI pain severity score at Day 360.
- Change from baseline in SF-BPI pain interference score at Day 360.
- Proportion of participants with clinically relevant change in SF-BPI pain severity score from baseline to Day 360.
- Proportion of participants with clinically relevant change in SF-BPI pain interference score from Baseline to Day 360.

The applied summary measure will be described for each endpoint in the respective section. The handling of intercurrent events is described in [Section 2.6.3](#).

2 Statistical methods

2.1 Data analysis general information

Data will be analyzed by CCI on behalf of Novartis using latest version of SAS available with CCI according to the data analysis.

Final analysis will be conducted after all participants either completed the study or discontinued early and database was locked. Final analyses will be reported in the Final CSR. No interim analysis is planned for this study.

Unless otherwise stated, summary tables, figures and listings will include all participants of the considered analysis set, respectively.

Categorical data will be presented as frequencies and percentages. For continuous data, number of participants, mean, standard deviation, median, 25th (Q1) and 75th (Q3) percentiles, minimum, and maximum will be presented.

Details on number of decimals displayed are provided in the TFL-Shells.

2.1.1 General definitions

2.1.1.1 Investigational treatment

The investigational drug is inclisiran.

The formulation is 300 mg inclisiran sodium (equivalent to 284 mg inclisiran) in 1.5 mL solution given as subcutaneous injection at Day 1, 90 and 270 by a delegated healthcare professional at the study site. The inclisiran-matching placebo is also given in 1.5 mL solution.

[figure not shown]
Additionally, at baseline visit all participants' background statin will be switched to rosuvastatin, which is considered open label study treatment and AxMP. Participants already on rosuvastatin at screening can be included up to a maximum of 10%. The starting dose for rosuvastatin will be 5 mg or 10 mg daily (per local SmPC and at discretion of the Investigator), with the dosage up titrated at each visit until the participants MTD or LDL-C target is achieved. Participants already receiving their MTD rosuvastatin prior to baseline will continue on their current dose in the treatment period.

The term blinded investigational treatment is used throughout the document and refer to the injection of double-blind treatment, i.e. Inclisiran/Placebo. The term open label study treatment refers to rosuvastatin.

2.1.1.2 Additional lipid lowering therapies

After randomization, if a participant receives their rosuvastatin MTD for at least 30 consecutive days and the participant is still not at their individual LDL-C target, the LLT must be further escalated as per recommended process (see [Figure 2-1](#) here and Section 3.4 in Protocol for further information).

Figure 2-1 Recommended treatment scheme based on ESC/EAS guidelines in combination with relevant HTA requirements

(+) Please refer to Section 3.4 in Protocol

* If indicated as per (local) SmPC

2.1.1.3 Treatment arms

The study consists of two treatment arms. Study participants will be assigned to one of the following treatment arms based on randomization in a ratio of 1:1:

- Inclisiran sodium 300 mg s.c.,
- Corresponding placebo.

The investigational treatment duration is planned for 360 days.

2.1.1.4 Study days

Study days will be calculated with respect to the first dose of investigational treatment.

The first day of administration of investigational treatment (first dose) is defined as Day 1. Day -1 will be the day before Day 1. Day 0 does not exist.

For assessment collected on or after Day 1, the study day is calculated as the difference between the date of assessment and the date of first dose plus 1 (= date of assessment – date of first dose + 1), while the study day for assessments prior to the first dose will be calculated as the difference between the date of assessment and the date of first dose (= date of assessment – date of first dose).

Duration of an event (e.g. adverse event, hospitalization) is calculated as the difference between the end and the start date of the event plus 1 (= event end date – event start date + 1).

2.1.1.5 Baseline

Baseline value is defined as the last non-missing value prior to the start of the treatment period, which means prior to the first injection of the blinded investigational treatment. If the date of assessment is the same as date of first injection but time is not available for comparison, the assessment is assumed to be prior to the administration of blinded investigational treatment. Questionnaires assessments at Day 1 are considered as baseline irrespective of time collected. Participants pain diary is not collected prior to first injection of the blinded investigational treatment, therefore baseline is not defined for the same.

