Enter patient visit into IRT	X						X	X	X	X	X ⁴	X	X	X	X		X	X	

Period	Screening	Run-In				Baseline		Treatment										Follow-up call	
Visit Name	Screening ¹	Run-In Period ²				Baseline ³		Treatment								Prior to PCSK9mAb switch ⁵	Unscheduled	EOT/EOS ²²	Follow-up call +30 days
Days	-144 to -130	-130	-100	-70	-40	-10	1	30	60	90	120 ⁴	150	210	270	330	UNS	UNS	360	390
Randomization							X												
Dispense inclisiran/placebo							X			X				X					
Dispense rosuvastatin							X	X	X	X	X ⁴	X	X	X	X		X		
Rosuvastatin compliance								X	X	X	X ⁴	X	X	X	X		X	X	
AEs/SAEs	X	X	X	X	X		X	X	X	X	X ⁴	X	X	X	X		X	X	S ⁷
Pregnancy Test (serum) ⁸	X																		
Pregnancy Test (urine) ⁹		X	X	X	X		X	X	X	X	X ⁴	X	X	X	X		X	X	
Physical Examination	S ⁷						S ⁷			S ⁷				S ⁷				S ⁷	
Body Height	X																		
Body Weight	X						X												
Vital Signs	X			X			X	X		X		X	X	X	X		X	X	
Fasting LDL-C assessment ¹⁰			X	X	X			X	X	X	X ⁴	X	X	X	X		X		
Fasting Lipid Profile ¹¹	X					X			X	X		X			X			X	
Fasting Lp(a) ¹²	X					X				X								X	
PCSK9 levels ¹³							X									X		X	
Clinical Chemistry ¹⁴	X			X		X				X		X	X	X	X			X	
Limited chemistry ¹⁵		X	X		X			X	X		X ⁴						X		

Period	Screening	Run-In				Baseline		Treatment											Follow-up call
Visit Name	Screening ¹	Run-In Period ²				Baseline ³		Treatment								Prior to PCSK9mAb switch ⁵	Unscheduled	EOT/EOS ²²	Follow-up call +30 days
Days	-144 to -130	-130	-100	-70	-40	-10	1	30	60	90	120 ⁴	150	210	270	330	UNS	UNS	360	390
Hematology ¹⁶	X					X						X						X	
Urinalysis ¹⁷	X					X						X						X	
Pain Diary ¹⁸							X	X	X	X	X	X	X	X	X		X	X	
SF-BPI ¹⁹	X						X	X	X	X	X ⁴	X	X	X	X		X	X	
GSRS ¹⁹							X	X	X	X	X ⁴	X	X	X	X		X	X	
SF-36 ¹⁹	X						X			X			X					X	
WIIQ ^{19,20}							X			X								X	
Mac New ^{19,21}							X			X								X	
TSQM ¹⁹							X			X								X	
Safety Follow up Call																			S ⁷

X Assessment to be recorded in the clinical database or received electronically from a vendor

¹ Central Lab results will be needed to confirm eligibility at the screening visit.

² Optional visit only for participants that require a statin up-titration after screening in order to reach their individual MTD, run-in-period

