³ The Baseline visit may be split into 2 visits, planned approximately 10 days apart. Participants not randomized within 7 days of screening or coming from run-in will have Day -10 visit which will only consist of Central lab draws. The investigator may schedule the Baseline (Day 1) visit, after Central lab results are received and eligibility confirmed.

⁴ Only if necessary, Optional visit for titration of rosuvastatin, treatment period

⁵ This is not required to be a stand-alone visit: This is a reminder to investigators to draw a blood sample, to measure levels of PCSK9, prior to switching a participant to a PCSK9 mAb. Timing for this visit will vary, depending on the timing of treatment switching and will not be applicable for all participants. In case PCSK9 samples were taken at an unplanned visit, the sampling can be recorded at this visit

⁶ Record any surgeries or medical procedures since the prior visit.

⁷ S: Record in Source Document only (send paper SAE form to safety when SAE is reported)

⁸ Only in women of childbearing potential. Serum tests will be sent to the Central lab for analysis.

⁹ Only in women of childbearing potential. Performed locally, prior to any dosing, using central laboratory kit supplies.

¹⁰ LDL-C can be assessed locally at the site via a provided LDL-C point of care device. These local results will be used for LLT decision making. In the event the assessment cannot be completed with the LDL-C point of care device, LDL-C will be assessed by central lab (unscheduled visit).

¹¹ LDL-C, ApoB, non-HDL-C, total cholesterol, triglycerides, and HDL-C. Performed by the central lab.

Period	Screening	Run-In					Baseline		Treatment										Follow-up call
Visit Name	Screening ¹	Run-In Period ²					Baseline ³		Treatment							Prior to PCSK9mAb switch ⁵	Unscheduled	EOT/EOS ²²	Follow-up call +30 days
Days	-144 to -130	-130	-100	-70	-40	-10	1	30	60	90	120 ⁴	150	210	270	330	UNS	UNS	360	390

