
8.1 Screening

Screening activities ([Table 8-1](#)) must be initiated only after the ICF (and assent if applicable) has been signed. A participant may go directly from the screening visit to the baseline visit, if they meet the criteria, as outlined in [Section 3.1](#). In this case the screening period may last up to 14 days. If the time between the screening labs and randomization is less than or equal to 7 days, then the labs do not need to be repeated and the screening labs will function as both the screening and baseline labs.

A participant who enters screening but is determined not eligible will be considered a screen failure. The investigator may consider re-screening the participant at a later time if he/she believes that the participant's condition has changed and they may potentially be eligible. In this case, a new participant number will be allocated to the participant and he/she will need to re-perform all Screening Visit procedures. A participant may be re-screened once. A minimum of 2 weeks must elapse between screen failure and re-screening. The participant must provide new written informed consent before being re-screened.

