2.1.1.7 Visits

Measurements will be collected without windowing as defined in the protocol. Analysis windows will be used for analysis of the data as outlined in [Table 2-1](#).

Based on the study day a scheduled or unscheduled visit is performed, the visit will be allocated to the analysis visit within the corresponding analysis visit window. E.g., if the Day 30 visit of a participant is delayed and occurs on day 33 it will be allocated to analysis visit Day 30. In the case of deviations from the visit schedule, or due to unscheduled visits, several assessments of a participant may fall in a particular analysis window (either scheduled or unscheduled).

If two measurements are allocated to the same analysis window and one is scheduled and the other unscheduled, the scheduled visit will be prioritized regardless of the difference to the target day (even if the unscheduled visit is closer to target day). If at least two scheduled or at least two unscheduled visits are allocated to the same analysis window, the measurement closest to the target day/time will be used. In the event that two measurements are taken equally apart (e.g., one day before target date and one day after) and both are either scheduled or unscheduled the last one will be used.

In case an analysis visit for a specific assessment is not planned (e.g., vital signs at Day 60), the time span (in days) between two visits is split equally and mapped to the former or consecutive analysis visit window, respectively.

The mapped visits will be used in the 'by visit' analysis as allocated. However, the listings will contain all information regardless if the collected data is based on a mapped or not-mapped, scheduled or unscheduled visit.

Table 2-1 Analysis visit windows based on study days

Analysis window (study days)									
Analysis Visit	SF-BPI, GSRS, Clinical chemistry (if also in Limited Chemistry)	Clinical Chemistry (and not in Limited Chemistry)	Fasting lipid profile (includes LDL-C for efficacy analyses)	Hematology, Urinalysis	Fasting Lp(a)	PCSK9	Vital signs	SF-36	WIQ, Mac New, TSQM
Pre-dose	<= 1 pre-dose	<= 1 pre-dose	<= 1 pre-dose	<= 1 pre-dose	<= 1 pre-dose	<= 1 pre-dose	<= 1	<= 1	<= 1
Day 30	30 [1 post-dose, 45]	30 [2, 60]	.	.
Day 60	60 [46, 75]	.	60 [1 post-dose, 75]
Day 90	90 [76, 120]	90 [1 post-dose, 120]	90 [76, 120]	.	90 [1 post-dose, 225]	.	90 [61, 120]	90 [2, 150]	90 [2, 225]

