2.3.2 Demographics and other baseline characteristics

The following participant demographic and baseline characteristics will be summarized descriptively by treatment group for the FAS:

- Age (years)
- Age groups (18 - <25 years, 25 - <45 years, 45 - <65 years, 65 - < 75 and ≥ 75),
- Age groups (18 - <65 years, 65 - < 75 and ≥ 75),
- Sex (male, female, unknown, undifferentiated),
- Country (Germany, Estonia, Latvia, Czech Rep, Spain, France, Poland, Bulgaria)
- Height (cm)
- Body weight (kg)
- BMI (kg/m^2), calculated as weight in kg divided by (height in m)²
- BMI group (< 18.5 kg/m^2 , 18.5 - <25 kg/m^2 , 25-<35 kg/m^2 , ≥ 35 kg/m^2)
- Statin use at baseline visit (% of participants on respective statin),
- Statin dose intensity at baseline visit
- CV risk category (high, very high)
- CV disease history, including but not limited to the following:
 - Myocardial Infarction
 - Unstable Angina
 - Stable Angina
 - Ischemic Stroke
 - Non-Ischemic Stroke
 - Trans ischemic Attack
 - Peripheral Artery Disease
 - Prior PCI
 - Prior stent implantation (Coronary)
 - Prior CABG
 - Primary Dyslipidaemia/ Hyperlipidaemia
 - Familial Hypercholesterolemia
 - Hypertension
 - Heart Failure
 - Atrial Fibrillation
 - Supraventricular Tachycardia

- Diabetes Mellitus
- Diabetic Retinopathy
- Diabetic Nephropathy
- Diabetic Neuropathy
- Alcohol history (Current, Never, Former)
- Smoking and vaping history (Current, Never, Former)
- Fasting Lipid profile
 - Lp(a) (nmol/L)
 - ApoB (μmol/L)
 - LDL-C (mg/dL)
 - HDL-C (mmol/L)
 - non-HDL-C (mmol/L)
 - total cholesterol (mmol/L)
 - triglycerides (mmol/L)
- relevant laboratory tests (Central lab)
 - AST (U/L)
 - ALT (U/L)
 - total bilirubin (μmol/L)
 - CK (U/L)
 - Creatinine Clearance (U/L)
 - eGFR (mL/min/1.73m²),
 - fasting glucose (mmol/L)
 - HbA1c (%)
- vital signs
 - SBP (mmHg),
 - DBP (mmHg),
 - Pulse (bpm)

Baseline values corresponding to laboratory measurements in the lipid panel refer to assessments collected on Day 1 of the study (before the first administration of the blinded investigational treatment).

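### SAP Table 2-1 windows SF-BPI and GSRS like laboratory tests, against the Day 1 questionnaire baseline rule in SAP 2.1.1.5; separately, the lipid baseline wording names a Day 1 sample that is not scheduled

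*SAP*

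**What the plan says.** **Questionnaires.** SAP 2.1.1.5 gives a general rule, "Baseline value is defined as the last non-missing value prior to the start of the treatment period", and then a specific one: "Questionnaires assessments at Day 1 are considered as baseline irrespective of time collected". SAP 2.1.1.6 classes everything performed at or after the start of the injection as post-baseline and makes no exception for questionnaires. In Table 2-1 (SAP 2.1.1.7), SF-BPI and GSRS share a column with the chemistry tests. Its pre-dose window ends on Day 1 before dosing, and its Day 30 cell begins "30 [1 post-dose, 45". The columns for SF-36 and for WIQ, MacNew and TSQM are different: they accept all of Day 1 as pre-dose and start the next window on day 2.

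**Lipids.** SAP 2.3.2 states: "Baseline values corresponding to laboratory measurements in the lipid panel refer to assessments collected on Day 1 of the study". Protocol 12.2 says the same. Protocol Table 8-1, footnote 3, says that participants not randomized within 7 days of screening, or coming from run-in, "will have Day -10 visit which will only consist of Central lab draws". For those randomized within 7 days, Protocol 8.1 says that "the screening labs will function as both the screening and baseline labs".

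**The concern.** Change from baseline in the SF-BPI severity and interference scores is tested at Day 360 as H05 and H06 (SAP 2.6.2.4). Baseline SF-BPI is both the reference for the change and a covariate in the repeated-measures model. The SAP should therefore say in one way only which record is baseline. As written, a Day 1 questionnaire completed after the injection gets two different labels, and no text says whether Table 2-1 or 2.1.1.5 takes precedence. A programmer would have to choose. One possible result is that the same record serves as both baseline and the Day 30 outcome.

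The lipid wording raises a similar doubt. Baseline LDL-C is the denominator and a covariate for H02 (SAP 2.6.2.1), and two places tie the lipid baseline to a draw that is not in the visit schedule.

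**Working it through.** No sample size, power or alpha figure depends on this point. The check sets the rules side by side and traces one record through them.

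**1. Which label does a Day 1 questionnaire receive?**

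| Day 1 record | SAP 2.1.1.5 | SAP 2.1.1.6 | Table 2-1, SF-BPI/GSRS | Table 2-1, SF-36 and WIQ/MacNew/TSQM |
|---|---|---|---|---|
| Before injection | Baseline | Not post-baseline | Pre-dose | Pre-dose |
| Time-stamped after injection | Baseline | Post-baseline | Day 30 | Pre-dose |

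The rules differ only in the second row. A Day 1 record with no time is assumed to precede the injection (SAP 2.1.1.5), so it causes no conflict.

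**2. Are the other limits of the SF-BPI column sound?** SAP 2.1.1.7 splits the time between planned visits equally. The midpoints for the analysis visits are (30+60)/2 = 45, (60+90)/2 = 75, (90+150)/2 = 120, (150+210)/2 = 180, (210+270)/2 = 240, (270+330)/2 = 300 and (330+360)/2 = 345. All match Table 2-1. The only fault is where the pre-dose window ends and the Day 30 window begins.

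**3. When would the Day 1 record become the Day 30 value?** Among scheduled records in one window, the closest to target is used. The Day 1 record is |1 − 30| = 29 days from target. Any other record in the window lies between day 2 and day 45, so it is at most |2 − 30| = 28 days away, or |45 − 30| = 15 at the upper end. A scheduled Day 30 assessment in the window therefore always displaces the Day 1 record. If there is none, the Day 1 record is used. An unscheduled SF-BPI in the window would not prevent this, because scheduled visits take priority whatever their distance. If the record also serves as baseline under 2.1.1.5, the Day 30 change is exactly 0, where SAP 5.5.3 would otherwise impute a missing value.

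**4. How does this reach H05 and H06?** Both are tested at Day 360. Given that 2.1.1.5 fixes the baseline, a misfiled Day 30 value acts only indirectly: as a predictor when later missing visits are imputed (SAP 5.5.3), and through the within-participant covariance of the model.

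**5. Lipids.** In Table 8-1 the row "Fasting Lipid Profile ¹¹" is marked at screening, Day -10 and Days 60, 90, 150, 330 and 360. The site LDL-C row has no Day 1 mark either. Scheduled Day 1 lipid draws: 0. Three other places support this reading: footnote 3, Protocol 8.1, and the lipid column of Table 2-1, whose post-dose visits are Days 60, 90, 150, 330 and 360. That column, which covers the LDL-C used for efficacy, takes any value up to Day 1 before dosing. With the general rule in 2.1.1.5, it selects the Day -10 value, or the screening value when that was drawn within 7 days of randomization.

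**The case against.** The strongest reply is that the documents already settle the matter. SAP 2.1.1.5 has a sentence written for the late Day 1 questionnaire, whereas Table 2-1 only allocates records to visits and labels its first row pre-dose, not baseline. The specific definition should prevail. Protocol 6.3.2 also places the injection after all other assessments of the visit, and Protocol 8.5.1 asks for questionnaires before clinical assessments, so a post-injection SF-BPI is out of protocol order. GSRS is exploratory.

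Most of this stands. It limits how often the conflict arises and makes 2.1.1.5 the natural reading. It does not remove the conflict: Table 2-1 and 2.1.1.6 still label the record as post-baseline, and the 2.1.1.5 sentence has a purpose only if some Day 1 questionnaires are late.

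A reader might go further in four ways that the documents do not support:

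- *Baseline LDL-C would be imputed for everyone.* SAP 5.5.3 imputes missing baselines. Under 2.1.1.5 the Day -10 or screening value is the baseline, so it is not missing.
- *Two lipid rules give one participant two different baselines.* With no scheduled Day 1 draw, there is no competing scheduled value.
- *SF-BPI baseline would revert to screening, and GSRS would have none.* This follows only if Table 2-1 is allowed to override the specific sentence in 2.1.1.5.
- *A stated number of participants is affected.* The documents give no rate of late Day 1 questionnaires, so any such number would rest on an invented percentage.

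**Conclusion.** Two inconsistencies stand in the current text, and both are limited in reach.

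The first is internal to the SAP. The SF-BPI/GSRS column of Table 2-1, together with 2.1.1.6, contradicts 2.1.1.5 for any Day 1 questionnaire time-stamped after the injection. Such a record becomes the Day 30 value only when there is also no scheduled Day 30 assessment. The number affected is unknown and should be low if sites follow the protocol order. The effect on the Day 360 tests of H05 and H06 is probably small. That is a judgement from how the record enters the analysis, not a calculated figure. Correction is still worthwhile, because the instrument supports two confirmatory hypotheses and the windowing rule misfiles a record that the SAP itself defines as baseline.

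The second is one of wording. SAP 2.3.2 and Protocol 12.2 name a Day 1 lipid sample that is not scheduled. It bears on the description of baseline characteristics, not on the H02 analysis, which has a usable baseline under 2.1.1.5 and the lipid window of Table 2-1.

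**What to change.** 1. In SAP Table 2-1, take SF-BPI and GSRS out of the chemistry column and give them their own, with baseline `<= 1` and Day 30 `[2, 45]`. All later windows stay as they are, and the chemistry column is unchanged.
2. In SAP 2.1.1.6, add that Day 1 questionnaires are baseline under 2.1.1.5 and are not post-baseline measurements.
3. In SAP 2.3.2, replace the Day 1 lipid sentence with the 2.1.1.5 rule: the last central-laboratory value before the first injection of blinded treatment. In practice this is the Day -10 draw, or the screening draw when it was taken 7 days or less before randomization.
4. In SAP Section 4, record the departure from Protocol 12.2. That section lists changes to the protocol-specified analyses and does not mention this one.

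The cost is one table column and a few sentences, with no new data and no change of model. The changes should be made before database lock, so that the derivation is fixed before treatment codes are known.
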